Study Rationale:	
Old age is associated with declining skeletal muscle mitochondrial bioenergetics with related decrements in cardiorespiratory fitness (CRF) and physical function that predispose to frailty, disability, and diminished quality of life. While exercise training may moderate and possibly even reverse declines in mitochondrial bioenergetics, and bring about clinical benefit, the potential for such improvement is typically confounded by exercise intolerance with early fatigability that results from the same age-related mitochondrial declines. Consequently, sedentariness is endemic and insidious among the growing population of older adults.
 
The principal rationale for the trial is innovative as it is oriented to sedentariness and related fatigability, and a pharmacological means to moderate them. It targets a mechanistic underpinning to fatigability as a symptom related to limitations in mitochondrial bioenergetics and vascular function and explores the utility of nitrite supplements as a novel means to improve the underlying physiology and clinical correlates.

Study Objectives:	To assess the impact of nitrite supplements on mitochondrial respiration, with associated focus on mitochondrial energetics and muscle perfusion, and to complete preliminary analysis on clinical correlates.
Study Hypotheses:	
 
• We hypothesize that nitrite will increase skeletal muscle mitochondrial energetics.
 
• We hypothesize that improved skeletal muscle mitochondrial respiration will relate to both direct enhancement of mitochondrial respiration as well as improved skeletal muscle perfusion.
 
• We hypothesize that changes in skeletal muscle mitochondrial respiration will correspond to improved CRF, reduced fatigability and improved PA.
 

Study Aims:	
Aim 1: To show efficacy of 12-weeks of sodium nitrite treatment to improve mitochondrial energetics.
 
Aim 2: To show efficacy of 12-weeks of sodium nitrite treatment to improve skeletal muscle perfusion.
 
Aim 3: To explore the effects of nitrite-induced changes in mitochondrial energetics on CRF and metrics of clinical function.
 
Overall, this protocol lays a mechanistically-oriented foundation for future studies to definitively assess the utility of nitrite treatment as an important therapeutic option for the growing burden of sedentariness in old age

Study Design:	Prospective, randomized, placebo-controlled, double-blinded trial at 2 clinical sites to study the utility of a 12-week intervention (oral nitrite capsules vs. placebo) in older (age $\geq 70$ years) healthy, sedentary adults (<1 hour of structured PA per week).
Planned Sample Size:	70 participants total
Duration of Treatment:	14 weeks (12 weeks of Intervention with 2 weeks of Post-intervention testing)
Major Inclusion Criteria:	
 
• Age <math>\geq 70</math> years
 
• Sedentary (<1 hour/week of volitional exercise activity)
 
• Clinically stable (euvolemic; baseline HR <math><100</math> bpm) and without hospitalization or invasive cardiac procedure for 6 weeks
 

Major Exclusion Criteria:	See complete list in section 3.3

Study Endpoints:	Overall, study endpoints pre- and post- nitrites will include: 

Aim 1: Mitochondrial energetics: ex vivo assessments of permeabilized skeletal muscle fiber respiration with Oroboros (primary outcome) and in vivo assessments of skeletal muscle ATP production with phosphorus-magnetic resonance spectroscopy (<math>^{31}\text{P}</math>-MRS).

Aim 2: Skeletal muscle perfusion: near infrared spectroscopy (NIRS) to oxygenation and perfusion.

Aim 3: Exploratory assessment of clinical correlates. Symptom-limited (maximal) CPET will be used to assess CRF (measured as peak oxygen consumption [<math>\text{VO}_2</math>]). Submaximal CPET (resistance which corresponds to 60%-80% peak <math>\text{VO}_2</math>) to exhaustion to assess endurance. Steady-state walking test on a level treadmill (with gas exchange) to assess walking efficiency and fatigability. Other functional measures include 400-m corridor walk, short physical performance battery (SPPB), handgrip strength, and daily physical activity (PA).

-------------------------	--

## 1. STUDY OBJECTIVES, SPECIFIC AIMS, BACKGROUND, AND SIGNIFICANCE

### 1. STUDY OBJECTIVES

**PRIMARY OBJECTIVE:** To assess the impact of nitrite administration on mitochondrial respiration, with associated focus on mitochondrial bioenergetics and muscle perfusion.

#### 1.2 SPECIFIC AIMS

Two-site randomized controlled trial to clarify the impact of a 12-week course of nitrite supplements versus placebo on mitochondrial energetics in older sedentary adults. We will take an integrative physiology approach to determine the effect of nitrite therapy on a comprehensive assessment of mitochondrial energetics, skeletal muscle vascular function, and whole-body physical function (cardiorespiratory fitness [CRF], exercise endurance, strength, balance, and daily physical activity [PA]) and fatigability.

**Aim 1:** To show efficacy of 12 weeks of sodium nitrite treatment to improve mitochondrial energetics.

- We hypothesize that compared to placebo, the participants receiving nitrite supplements will show an improvement in:

H1a: Skeletal muscle mitochondrial respiration, efficiency (high resolution respirometry [primary outcome]) and adenosine triphosphate (ATP) production (phosphorus-magnetic resonance spectroscopy)

H1b. Morphology and molecular underpinnings of muscle energetics (Direct Immunofluorescence and light microscopy of mitochondrial structure, RNA-Seq and Western Blot)

**H1c: Platelet mitochondrial respiration (Seahorse), i.e., an analysis to clarify whether platelets can be used as a surrogate to skeletal muscle to assess equivalent changes in mitochondrial bioenergetics**

**Aim 2:** To show efficacy of 12 weeks of sodium nitrite supplements to improve skeletal muscle perfusion.

- We hypothesize that, compared to placebo, the nitrite group will show a greater improvement in:

**H2a:** Tissue oxygenation, as measured using near infrared spectroscopy (NIRS) during exercise.

**Aim 3:** To explore the effects of nitrite-induced changes in mitochondrial energetics on CRF and metrics of clinical function.

- We hypothesize that, compared to placebo, the participants receiving nitrite supplements will show a greater improvement in:

**H3a:** Increased CRF (peak oxygen uptake [ $\text{VO}_2$ ] achieved during progressive resistance on a cycle ergometer), increased endurance (duration of exercise at fixed resistance 60%-80% peak  $\text{VO}_2$  intensity), increased efficiency of walking (decreased  $\text{VO}_2$  at steady-state [1.5 mph] and self-paced walking), increased 400-meter corridor walk, increased SPPB score; increased handgrip strength, increased PA (accelerometry), and decreased fatigability (during steady-state walking and 400-meter corridor walk respectively).

**H3b:** Changes in mitochondrial energetics and skeletal muscle perfusion induced by nitrite will be associated with changes in daily activity (measured by accelerometry), and fatigability (measured by rate of perceived exertion during steady-state [1.5 mph] walking).

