### **1.3. BACKGROUND AND RATIONALE**

Our multi-disciplinary team has published seminal work indicating that mitochondrial bioenergetics and CRF are significant determinants of physical function in older adults. In parallel efforts, we showed efficacy of chronic nitrite supplements to improve mitochondrial bioenergetics in older sedentary adults. Only one month of nitrite supplements significantly improved ex vivo assessments of mitochondrial energetics in skeletal muscle biopsies, concomitant with increased skeletal muscle sirtuin-3 expression, a nicotinamide adenine dinucleotide (NAD) dependent lysine deacetylase and key regulator of mitochondrial metabolism. These key data reinforce the premise that nitrite enhances vital mitochondrial metabolism in older adults. Moreover, improvement in muscle energetics in nitrite-treated older adults was linked with increased exercise efficiency as evidenced by reduced  $\text{VO}_2$  during submaximal steady-state walking. These data support our overarching hypothesis that nitrite supplements will make physical function easier such that PA will increase.

Older adults represent the fastest growing demographic in the population of the United States and constitute a unique and growing healthcare challenge. Aging is associated with an inexorable decline in CRF and decreased PA with harmful implications that include increased vulnerabilities to disease, frailty, reduced independence, diminished quality of life as well as escalating healthcare costs. Yet despite typical age-related declines, many older adults are able to mitigate the rate of decline in fitness and activity, and to thereby better preserve healthfulness and well-being. While behavioral and community interventions are often pursued as vital strategies to optimize activity and health, for many older adults such good intentions are stymied by intrinsic age-related exercise intolerance and

early fatigability that undermine goals to be active. Our protocol responds to such challenges by focusing on the utility of nitrite supplementation to enhance skeletal muscle mitochondrial energetics in older sedentary adults. We will build on our exciting preliminary data to clarify if mitochondrial benefits extend to improved physical function, including CRF, endurance, strength, balance, and PA.

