- The skeletal muscle mitochondrial assessments will be coupled with an analysis of platelet mitochondrial energetics (Seahorse) to determine the utility of platelet measurements to be applied as (1) a novel and convenient biomarker of mitochondrial energetics.
- NIRS will be used to assess: (1) skeletal muscle mitochondrial metabolic performance profile during the hypoxic stress by gauging perfusion changes pre- and 12-week post-nitrite versus placebo. Clinical and Physiological assessments:

Fitness and Efficiency (1) CRF (peak VO2) on a progressive intensity cycle ergometer will clarify how changes in mitochondrial respirometry translate into systemic oxygen utilization, highlighting physiological linkage between cellular respiration and whole-body oxygen utilization and putative benefits of nitrite to improve these relationships; (2) VO2 at 60%-80% exercise resistance (watts) on a cycle ergometer until exhaustion will assess nitrite-mediated changes in endurance; (3) VO2

at a steady-state walking (1.5 mph) will assess nitrite-mediated changes in the efficiency of walking and associated perceived fatigability (changes in rated of perceived exertion); (4) 400-meter corridor walk (with portable gas exchange) will be used to assess overall capacity (disability), physical fatigability (slowing of walking speed), as well as the energy of walking.

Additional functional measures: (1) short physical performance battery (SPPB) to assess strength, balance, and an index of frail; (2) handgrip to assess strength; (3) daily activity (accelerometry).

Fatigability: Fatigability assessments are novel, and include both “perceived” (rate of perceived exertion [RPE]) during steady-state walking, as well as “performance” (energy consumed during a 400-meter corridor walk) subtypes.

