### **Pre-drug baseline study visits (Visits 1- 4)**

#### **Visit 1**

Participants will be encouraged to have a light meal prior to arrival.

1. Interval history, vital signs, and a brief physical exam.
2. Exercise testing:
  - a. **Cardiopulmonary Exercise Testing (CPET)**: A symptom-limited (maximal) graded cycle ergometer exercise test in association with air-gas-exchange, an optimal gauge of aerobic capacity will be conducted by trained research exercise physiologists. A study clinician will be immediately available if needed. A computerized cycle ergometer will be used to generate a symptom-limited exercise stimulus. ACSM criteria for starting and stopping will also be utilized. A face mask or mouthpiece will be positioned over the subject's mouth and nose during the exercise for gas exchange assessments. VO2, minute ventilation (VE)/exhaled carbon dioxide (VCO2) slope, and respiratory exchange ratio (RER) will be measured as well as hemodynamics (max HR and BP), time, and ECG waveforms). Any unexpected abnormalities will be reported to the participant's primary provider(s); continued participation in the study will require the primary provider's clearance. The rate of perceived exertion (RPE) will be completed during the CPET.
  - b. **400-meter corridor walk**: Participants will walk over a 400-meter course. During the 400-meter corridor walk, average VO2 per lap during steady-state

(2 minutes of plateaued  $\text{VO}_2$ ) will be used to calculate the energy cost of walking by normalizing the  $\text{VO}_2$  to lap gait speed (ml/kg/m).

- c. For participants with diabetes, they will be asked to bring their own glucometer to assess glucose before and after the CPET.
- d. **NIRS**: NIRS will be worn during the CPET and 400-meter corridor walk. Sensors will be placed on the skin of one leg to allow the non-ionizing, LED light source to assess tissue oxygenation and perfusion via measurements of the optical absorption of hemoglobin.
- e. **Accelerometry**: An ActiGraph wrist accelerometer will be worn during the 400-meter corridor walk to establish baseline activity parameters and during the CPET.

3. A battery of questionnaires will be administered.
  - a. The following questionnaires will be administered:
  - b. Community Healthy Activities Program for Seniors (CHAMPS)
  - c. Fried Frailty Index
  - d. EuroQol

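### Aim 2 claims improved muscle perfusion, but H2a measures NIRS tissue oxygenation, which can rise through lower oxygen use alone

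*Combined protocol and SAP*

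**What the plan says.** The Protocol Synopsis states Aim 2 as "To show efficacy of 12-weeks of sodium nitrite treatment to improve skeletal muscle perfusion", and section 1.2 repeats it. The only hypothesis listed under it is H2a: "Tissue oxygenation, as measured using near infrared spectroscopy (NIRS) during exercise".

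The NIRS signal is described in three ways. The Synopsis endpoints for Aim 2 give "near infrared spectroscopy (NIRS) to oxygenation and perfusion". Section 2.2.1, Visit 1, says the sensors "assess tissue oxygenation and perfusion via measurements of the optical absorption of hemoglobin". Section 1.4 uses NIRS to assess the "skeletal muscle mitochondrial metabolic performance profile during the hypoxic stress" and, in the same sentence, links this to perfusion changes before and after treatment. No section names a NIRS variable, a flow index, an occlusion or tracer method, or an adjustment for oxygen use.

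The analysis is in section 2.4.2, in the paragraph before the one labelled Aim 2. Perfusion outcomes get the same ANCOVA contrast of nitrite against placebo as the primary outcome, as the formal test of H2a-b. H2b is defined nowhere.

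On oxygen use, section 1.3 reports from earlier work that "improvement in muscle energetics in nitrite-treated older adults was linked with increased exercise efficiency as evidenced by reduced" VO2 in submaximal steady-state walking. H3a (section 1.2) predicts lower VO2 in steady-state and self-paced walking, and higher peak VO2 on the cycle. By section 2.2.1 (Visits 1 and 2) and the footnote to the timetable in 2.2.2, NIRS is worn in the maximal CPET, the submaximal CPET, the 400-meter walk and the 1.5 mph walk.

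**The concern.** The aim names one construct and the hypothesis measures another. Perfusion is delivery; tissue oxygenation is what remains after delivery and use have offset each other. That would matter little if treatment left oxygen use alone, but this trial predicts that nitrite changes it. Randomization does not help, because the change in use would itself be a treatment effect.

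Two errors follow. A positive H2a could be reported as better perfusion when the muscle merely needed less oxygen for the same work. A null H2a could be reported as no perfusion benefit when flow and use rose together.

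The Synopsis hypothesizes that respiration improves both directly and through perfusion, and H2a is the only planned functional evidence for the second route. Capillary density on biopsy (section 1.4) is structural and sits outside Aim 2. H3b then relates change in perfusion to activity and fatigability, so the ambiguity carries into Aim 3.

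**Working it through.** **The plan's own figure.** None exists for Aim 2 or NIRS. The only detectable difference for a treatment contrast (section 2.4.1: 71.80 pmol/min/mg, SD 97.61, 30 completers per arm) is for State 3 respiration. It reproduces (71.80 / 97.61 = 0.736; two-sample t-test power 0.800) but has no bearing here.

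**Direction of the signal, test by test**

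- *1.5 mph walk.* Work is fixed and H3a predicts lower VO2. Lower use at unchanged flow raises oxygenation.
- *400-meter walk.* I take this to be the self-paced test, since it is the only other walk with gas exchange. H3a again predicts lower VO2, and walking speed may itself change with treatment.
- *Submaximal CPET.* Resistance is fixed from the Visit 1 test. H3a predicts longer duration and states no VO2 change.
- *Maximal CPET.* H3a predicts higher peak VO2. Higher use offsets higher flow, so oxygenation may not rise.

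**How large the ambiguity could be.** The documents give no magnitude for NIRS, extraction or the VO2 change, so these inputs are assumptions: arterial saturation 97%, baseline extraction E of 50% to 80%, and a fall r in local oxygen use of 3% to 10%. By mass balance:

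- E is proportional to use / flow
- venous saturation = 0.97 × (1 − E)
- rise after a fall r in use at constant flow = 0.97 × E × r
- flow increase giving the same rise at constant use = 1/(1 − r) − 1

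Example with E = 60% and r = 5%: extraction becomes 0.60 × 0.95 = 0.57, and saturation rises by 0.97 × 0.60 × 0.05 = 2.91 points. The equivalent flow increase is 1/0.95 − 1 = 5.26%.

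| Baseline extraction | r = 3% | r = 5% | r = 10% |
|---|---|---|---|
| 50% | 1.46 | 2.42 | 4.85 |
| 60% | 1.75 | 2.91 | 5.82 |
| 70% | 2.04 | 3.40 | 6.79 |
| 80% | 2.33 | 3.88 | 7.76 |
| Equivalent rise in flow | 3.09% | 5.26% | 11.11% |

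Cells are points of venous saturation. In every cell a rise in flow gives the identical change, so oxygenation alone cannot tell the two apart.

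**Peak effort.** If use and flow both rise by 5% from E = 60%, extraction is 0.60 × 1.05 / 1.05 = 0.60. Saturation does not move although flow has improved.

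**The case against.** The strongest reply is that the documents do say NIRS gauges perfusion (Synopsis endpoints, section 1.4, Visit 1), and that the citation of H2b suggests a second Aim 2 hypothesis was intended. This stands in part. It would be wrong to infer that NIRS can say nothing about perfusion; the point concerns H2a as written, which is oxygenation alone. But a label does not define a variable, and H2b has no content to rely on.

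Several stronger readings are tempting and are not supported:

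- *That the earlier work already explains a rise in NIRS oxygenation.* Section 1.3 reports whole-body VO2 in walking. It gives no NIRS data and no local muscle oxygen use. It makes the alternative explanation plausible and does not prove it.
- *That the direct and perfusion routes cannot be separated at all.* Section 1.4 describes ex vivo respirometry as free of limits from substrate and oxygen supply, so the direct route has its own test. Only the perfusion half depends on NIRS.
- *That Aim 1 predicts higher oxygen use during exercise.* State 3 respiration in permeabilized fibers is a capacity measured outside the body. The case for higher use rests only on the peak VO2 prediction in H3a.

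It is also fair that matched-work recordings, with gas exchange, are already planned (Visit 2, repeated at Visit 7). What is missing is a statement that H2a rests on them and a conclusion limited to what they measure. Finally, the arithmetic concerns venous saturation, not the NIRS tissue signal. It shows ambiguity, not the probability of a wrong conclusion.

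**Conclusion.** The concern holds for H2a as written. A treatment difference in NIRS tissue oxygenation would show a change in the balance of supply and use; by itself it would establish neither Aim 2's perfusion claim, nor the perfusion half of the Synopsis hypothesis, nor the perfusion correlate in H3b. A null result at peak effort would not exclude better perfusion.

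On the assumed values, plausible-looking changes of 1.5 to 8 saturation points have two equally good explanations. The range depends on the assumptions; the inability to separate the explanations does not. It needs only that oxygenation depends on both delivery and use, and that treatment may alter use, as H3a predicts.

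This is worth correcting but limited: section 2.4.2 makes H1a the primary test, and nothing here touches it.

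**What to change.** 1. Word the Aim 2 and H2a conclusion as tissue oxygenation (supply-use balance), not perfusion, and carry that wording into H3b.
2. Name the NIRS variable and base the H2a test on matched work: the 1.5 mph walk and the submaximal CPET at the resistance set from Visit 1. State that Visit 7 uses the same resistance as Visit 2 and, because the ride goes to exhaustion, compare at the same elapsed time. Treat peak and self-paced recordings as descriptive.
3. Report the simultaneous VO2 change beside the oxygenation contrast. Matching work removes differences in work done but not an efficiency effect. VO2 here is whole-body, so it aids interpretation and is not a correction for local use.
4. Define H2b or delete it.
5. If the device gives total hemoglobin, report it as supportive evidence on blood volume only. It is not a flow measure, so it should not be the condition for a perfusion claim.

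The cost is wording in the aims and in section 2.4.2; items 1 to 4 need no new visits or recordings. The downside is a more modest Aim 2. Retaining a perfusion claim would need a pre-specified measure of delivery, which the present plan does not contain.

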### **1.3. BACKGROUND AND RATIONALE**

Our multi-disciplinary team has published seminal work indicating that mitochondrial bioenergetics and CRF are significant determinants of physical function in older adults. In parallel efforts, we showed efficacy of chronic nitrite supplements to improve mitochondrial bioenergetics in older sedentary adults. Only one month of nitrite supplements significantly improved ex vivo assessments of mitochondrial energetics in skeletal muscle biopsies, concomitant with increased skeletal muscle sirtuin-3 expression, a nicotinamide adenine dinucleotide (NAD) dependent lysine deacetylase and key regulator of mitochondrial metabolism. These key data reinforce the premise that nitrite enhances vital mitochondrial metabolism in older adults. Moreover, improvement in muscle energetics in nitrite-treated older adults was linked with increased exercise efficiency as evidenced by reduced  $\text{VO}_2$  during submaximal steady-state walking. These data support our overarching hypothesis that nitrite supplements will make physical function easier such that PA will increase.

Older adults represent the fastest growing demographic in the population of the United States and constitute a unique and growing healthcare challenge. Aging is associated with an inexorable decline in CRF and decreased PA with harmful implications that include increased vulnerabilities to disease, frailty, reduced independence, diminished quality of life as well as escalating healthcare costs. Yet despite typical age-related declines, many older adults are able to mitigate the rate of decline in fitness and activity, and to thereby better preserve healthfulness and well-being. While behavioral and community interventions are often pursued as vital strategies to optimize activity and health, for many older adults such good intentions are stymied by intrinsic age-related exercise intolerance and

early fatigability that undermine goals to be active. Our protocol responds to such challenges by focusing on the utility of nitrite supplementation to enhance skeletal muscle mitochondrial energetics in older sedentary adults. We will build on our exciting preliminary data to clarify if mitochondrial benefits extend to improved physical function, including CRF, endurance, strength, balance, and PA.

